7.3.2.3. Overall Survival in the Follicular Lymphoma Population

Overall survival is defined as the time from randomization until death from any cause. All participants should be followed until death or until the end of study, whichever comes first, as specified in the Protocol.

The cause of death ("disease progression," "adverse event," or "other") will be summarized.

Participants who are not reported as a death at the time of the analysis cutoff will be censored at the earlier of the analysis cutoff and date of last known alive. The last known alive date is defined as the later of the last study visit and the date the participant was last known alive from the "Survival Follow-Up," "End of Treatment," and "End of Study" eCRFs. Partial death dates will be handled using the rules described in Section 4.1.4.

Overall survival will be compared and analyzed using stratified tests as described in Section 7.3 for PFS with FL in the FAS at the time of interim, primary, and final analysis. Participants will be censored at the last date they were known to be alive, regardless if a new antilymphoma therapy was started.

Post-treatment systemic antilymphoma therapies will be summarized and listed.

[figure not shown]
7.3.3. Currentness of Progression-Free Survival and Overall Survival Data

To assess the currentness of PFS data, the time from the last tumor assessment to the data cutoff date in months will be summarized by treatment group and overall for the FL population and the overall FAS. Participants who have a PFS event will be considered as current for this analysis.

Currentness of OS data will be summarized by treatment group and overall for the FL population and the overall FAS in months from the last known alive date to the data cutoff date. Participants who have a death event will be considered as current for this analysis.

7.3.4. Progression-Free Survival/Overall Survival Follow-Up Time

Follow-up time for PFS/OS will be defined from the date of randomization and will use the inverse of the censoring rules for PFS/OS. The median PFS/OS follow-up time and 95% CI will be estimated by reversed Kaplan-Meier method by treatment group and overall for the FL population and the overall FAS.

7.4. Analysis of Other Secondary Efficacy Parameters

7.4.1. Positron-Emission Tomography-Complete Response Rate in the FDG-Avid Overall Population

The PET-CR rate in the FDG-avid overall population (FL and MZL) will be compared and analyzed in the same manner as described in Section 7.3.2.2 for the PET-CR rate in the FDG-avid FL population.

7.4.2. Minimal Residual Disease-Negativity Rate at End of Treatment in the MRD-Evaluable Follicular Lymphoma Population and MRD-Evaluable Overall Population

The MRD-negativity rate is defined as the proportion of participants who achieved a negative MRD result in peripheral blood at the EOT. The threshold used for the analysis is 10^{-5} cells. Participants with no postbaseline assessment, or who did not achieve a negative MRD result will be classified as "non–MRD-negative." Analysis of the MRD-negativity rate at EOT will be performed for participants in the MRD-blood evaluable FL population and the MRD-blood evaluable overall population (FL and MZL).

The MRD-negativity in the 2 treatment groups will be compared and analyzed in the same manner as described in Section 7.3.2.2 for the PET-CR rate.

The MRD analysis will be performed using samples with a time interval of ≤ 5 days between sample collection and receipt by the laboratory to ensure sample integrity.

Reasons for missing MRD assessments will be summarized, for example, missed assessment, unevaluable assessment.

Sensitivity analysis will be performed on:

- Using peripheral blood sample at both C4 and C8 (in the MRD-blood evaluable population)
- Using bone marrow sample at EOT (in the MRD-bone marrow evaluable population)
- Using bone marrow sample at CR (in the MRD-bone marrow evaluable population)

Estimates of the MRD-negativity rate along with its exact 95% CIs using the Clopper-Pearson method will be calculated for each treatment group. No statistical comparison will be performed for this analysis.

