3. OBJECTIVES AND ENDPOINTS

Table 5 presents the objectives and endpoints.

Table 5: Objectives and Endpoints

Objectives	Endpoints								
Primary									
To compare the efficacy of tafasitamab and lenalidomide in addition to rituximab to the efficacy of placebo and lenalidomide in addition to rituximab in terms of PFS in participants with R/R FL.	PFS by INV assessment in the FL population, using the Lugano 2014 criteria (Cheson et al 2014). PFS is defined as the time from randomization to first documented disease progression, or death from any cause, whichever occurs first.								
Secondary									
Key Secondary Endpoints									
To compare the efficacy of tafasitamab and lenalidomide in addition to rituximab versus placebo and lenalidomide in addition to rituximab in terms of PFS in the overall population (FL and MZL).	PFS by INV assessment in the overall population (FL and MZL populations).								
To compare the efficacy of tafasitamab and lenalidomide in addition to rituximab versus placebo and lenalidomide in addition to rituximab in terms of PET-CR rate in FDG-avid FL participants and OS in the FL population.	 PET-CR rate by INV in the FDG-avid FL population, defined as a complete metabolic response at any time after start of treatment. OS in the FL population. 								
Other Secondary Endpoints									
To compare the efficacy of tafasitamab and lenalidomide in addition to rituximab versus placebo and lenalidomide in addition to rituximab.	 PET-CR rate by INV in the FDG-avid overall population. MRD-negativity rate (at thresholds of 10⁻⁴ and 10⁻⁵) at EOT in the FL and the overall populations. ORR by INV in the FL and overall populations. DoR by INV in the FL and overall populations. OS in the overall population. 								
To compare the efficacy between treatment groups based on IRC assessment.	 PFS by IRC in the FL and overall populations. ORR by IRC in the FL and overall populations. DoR by IRC in the FL and overall populations. 								
To evaluate QoL of tafasitamab and lenalidomide in addition to rituximab versus placebo and lenalidomide in addition to rituximab in the FL and overall population.	QoL as measured by the EORTC QLQ-C30, the EQ-5D-5L, and FACT-Lym tools in the FL and overall populations.								

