10.4.1.4. Analyses of Other Secondary Efficacy Endpoints

10.4.1.4.1. Positron Emission Tomography-Complete Response Rate in the Overall Population

The PET-CR rate in the overall FDG-avid population (FL and MZL) will be compared and analyzed in the same manner as described in Section 10.4.1.2.2 for the PET-CR rate in the FDG-avid FL population. The stratification factors will be those used for the PFS analysis on

the FL population and on the overall population, respectively (see Section 10.4.1.1 and Section 10.4.1.2.1).

10.4.1.4.2. Minimal Residual Disease-Negativity Rate at End of Treatment in the Follicular Lymphoma and Overall Population

The MRD-negativity rate is defined as the proportion of participants who achieved a negative MRD result at EOT. Participants with no postbaseline assessment or who did not achieve a negative MRD result will be classified as "non MRD-negative."

The MRD-negativity rate in the 2 treatment groups will be compared and analyzed in the same manner as described in Section 10.4.1.2.2 for the PET-CR rate. The stratification factors will be those used for the PFS analysis on the FL population and on the overall population, respectively (see Section 10.4.1.1 and Section 10.4.1.2.1). Analysis of the MRD-negativity rate at EOT will be performed for participants with FL and the overall population (FL and MZL) in the FAS.

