2.2. Study Objectives and Endpoints

Table 1 presents the objectives and endpoints.

Table 1: Objectives and Endpoints

Objectives	Endpoints
Primary	
To compare the efficacy of tafasitamab and lenalidomide in addition to rituximab to the efficacy of placebo and lenalidomide in addition to rituximab in terms of PFS in participants with R/R FL.	PFS by INV assessment in the FL population, using the Lugano 2014 criteria (Cheson et al 2014). PFS is defined as the time from randomization to first documented disease progression, or death from any cause, whichever occurs first.
Secondary	
Key Secondary Endpoints	
To compare the efficacy of tafasitamab and lenalidomide in addition to rituximab versus placebo and lenalidomide in addition to rituximab in terms of PFS in the overall population (FL and MZL).	PFS by INV assessment in the overall population (FL and MZL populations).
To compare the efficacy of tafasitamab and lenalidomide in addition to rituximab versus placebo and lenalidomide in addition to rituximab in terms of PET-CR rate in FDG-avid FL participants and OS in the FL population.	 PET-CR rate by INV in the FDG-avid FL population, defined as a complete metabolic response at any time after start of treatment. OS in the FL population.
Other Secondary Endpoints	
To compare the efficacy of tafasitamab and lenalidomide in addition to rituximab versus placebo and lenalidomide in addition to rituximab.	 PET-CR rate by INV in the FDG-avid overall population. MRD-negativity rate (at thresholds of 10⁻⁴ and 10⁻⁵) at EOT in the FL and the overall population. ORR by INV in the FL and overall populations. DOR by INV in the FL and overall populations. OS in the overall population.
To compare the efficacy between treatment groups based on IRC assessment.	 PFS by IRC in the FL and overall populations. ORR by IRC in the FL and overall populations. DOR by IRC in the FL and overall populations.

[figure not shown]
Table 1: Objectives and Endpoints (Continued)

Objectives	Endpoints	
Other Secondary Endpoints (continued)		
To evaluate QoL of tafasitamab and lenalidomide in addition to rituximab versus placebo and lenalidomide in addition to rituximab in the FL and overall population.	QoL as measured by the EORTC QLQ-C30, the EQ-5D-5L, and FACT-Lym tools in the FL and overal populations.	

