7.1. General Considerations

All efficacy analyses will be based on the FAS. Unless otherwise stated, all stratified efficacy analyses will use the same stratification factors as for randomization, which are specified in Section 3.1 and based on the data obtained from IRT.

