10.1. Changes to Protocol-Defined Analyses

The MRD-evaluable set analysis population was added in the SAP to support the sensitivity analysis for the summary of MRD-negativity rate.

The following analyses were added in the SAP to provide additional study information:

- Summary of currentness of PFS and OS data (see Section 7.3.3)
- Summary of PFS and OS follow-up time (see Section 7.3.4)
- Summary of time to objective response (see Section 7.5.4)
- Overall survival for PFS with FL for interim analysis (see Section 7.3.2.3 and Section 9.1.1)

As of SAP Amendment 2, the MRD-negativity rate threshold used other secondary efficacy analysis will be 10^{-5} and the threshold of 10^{-4} will be used for sensitivity (see Section 7.4.2).

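### The declared 10⁻⁴ MRD-negativity rate and the protocol's FAS-denominator rate have no planned analysis, and SAP Section 10.1 does not describe the current MRD analysis correctly

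*SAP*

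**What the plan says.** **Declared endpoint.** Protocol Table 5 lists, among the other secondary endpoints, "MRD-negativity rate (at thresholds of 10⁻⁴ and 10⁻⁵) at EOT in the FL and the overall populations". SAP Table 1 repeats it: "MRD-negativity rate (at thresholds of 10⁻⁴ and 10⁻⁵) at EOT in the FL and the overall population".

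**Analysis set.** Protocol Section 10.4.1.4.2 states: "Analysis of the MRD-negativity rate at EOT will be performed for participants with FL and the overall population (FL and MZL) in the FAS". SAP Section 7.1 gives the same general rule: "All efficacy analyses will be based on the FAS". The qualifier that follows in Section 7.1 concerns stratification factors and makes no exception to the FAS.

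**Planned analysis.** SAP Section 7.4.2 specifies peripheral blood at EOT and one cutoff ("The threshold used for the analysis is" 10⁻⁵). It compares the arms in the MRD blood-evaluable FL and overall populations, by the method used for the PET-CR rate. SAP Table 4 defines that set as FAS participants with at least one dose of study drug and a clone identifiable in Cycle 1 Day 1 blood.

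**Record of departures.** SAP Section 10.1 says that the evaluable set was added "to support the sensitivity analysis for the summary of MRD-negativity rate". It says that from Amendment 2 the secondary analysis uses 10⁻⁵, and that 10⁻⁴ "will be used for sensitivity (see Section 7.4.2").

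**The concern.** A declared secondary endpoint should lead to a planned result, and a departure from the protocol should be described correctly in the section that exists to disclose it. Here the endpoint tables, the general rule on analysis sets, the analysis section and the record of departures give different accounts of the same endpoint.

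A programmer following Section 7.4.2 and Appendix A would produce no 10⁻⁴ rate and no rate with the FAS as denominator. A reader relying on Section 10.1 would expect a 10⁻⁴ sensitivity result and would assume that the FAS is still the main denominator. At stake are whether the reported rate can be matched to the protocol-defined one, and whether the study report can account for both declared thresholds.

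**Working it through.** The documents give no expected MRD rate, evaluable share or power for this endpoint, so there is no figure to reproduce. The check is a comparison of current text, followed by an illustration of the denominator effect.

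**1. Threshold**

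| Place | 10⁻⁴ | 10⁻⁵ |
|---|---|---|
| Protocol Table 5 | declared | declared |
| SAP Table 1 | declared | declared |
| SAP 10.1 | sensitivity, citing 7.4.2 | secondary analysis |
| SAP 7.4.2, main analysis | absent | the only threshold |
| SAP 7.4.2, sensitivity list | absent | no other threshold named |

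The sensitivity list in Section 7.4.2 has three items: blood at Cycles 4 and 8, marrow at EOT, and marrow at complete response. None is stated to use 10⁻⁴. SAP Section 10.2.3 explains the gap: Amendment 3 took out the 10⁻⁴ EOT blood analysis because it would not be done. The 10⁻⁴ statement in Section 10.1 was not updated to match.

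**2. Analysis set**

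| Place | Set for the main MRD rate |
|---|---|
| Protocol 10.4.1.4.2 | FAS |
| SAP 7.1 and Table 4 | FAS for all efficacy analyses |
| SAP 7.4.2 | MRD blood-evaluable set |
| SAP Appendix A, Table 2.2.5.x | MRD blood-evaluable set |
| SAP 10.1 | evaluable set described only as support for sensitivity analysis |

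Appendix A's other MRD rate tables (2.2.6.x and 2.2.7.x) also use evaluable sets. Listing 2.6.16.x is labelled FAS, but a listing is not a planned rate comparison.

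**3. What the set does to the rate (illustration)**

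Let r be the rate in the evaluable set and e the evaluable share of the FAS. Protocol Section 10.4.1.4.2 counts anyone without a negative result as not MRD-negative. If participants without an identifiable clone are counted that way, then

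FAS rate = r × e.

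Both inputs are assumptions. With r = 60%:

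- e = 70%: 0.60 × 0.70 = 42%, which is 18 points lower.
- e = 90%: 0.60 × 0.90 = 54%, which is 6 points lower.

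With r = 50%, e = 60% gives 30% and e = 90% gives 45%, a shift of 20 to 5 points.

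**4. What the set does to the comparison**

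If e is the same in both arms, as randomization makes it in expectation, the FAS difference is (r_A − r_B) × e and the ratio of rates stays at r_A / r_B. The absolute difference shrinks, but no spurious difference arises.

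**The case against.** The case for leaving the analysis alone is substantial.

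- **Is the endpoint never reported?** A reader might infer this, but the documents do not support it. A 10⁻⁵ EOT rate is planned and compared between arms in the FL and overall populations.
- **Does Section 10.1 confine both changes to sensitivity analyses?** It does not. It openly makes 10⁻⁵ the threshold of the secondary analysis. Its account of the set is incomplete rather than false, because evaluable sets do also serve the listed sensitivity analyses.
- **Is this concealment or selective reporting?** The documents do not show that. SAP Section 10.2.2 logs that the threshold and denominator were addressed in Amendment 2, and Section 10.2.3 logs the removal of the 10⁻⁴ analysis. Protocol Section 6.3 keeps the study team blinded until the primary analysis.
- **Does the evaluable set bias the comparison?** This is not evident. The clonality criterion is assessed at Cycle 1 Day 1, the one-dose condition applies under the blind, and missing postbaseline results still count as failures. Counting participants with no trackable clone as failures would lower both arms' rates for a reason unrelated to treatment. Preferring the evaluable set as the main denominator is defensible.
- **Is much lost with 10⁻⁴?** A sample negative at 10⁻⁵ is also negative at 10⁻⁴, so the stricter threshold was kept. The 10⁻⁵ rate is thus a lower bound for the 10⁻⁴ rate, but it does not give the between-arm comparison at 10⁻⁴.

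These arguments remove any charge of bias or concealment. They do not remove the conflict in current text: SAP Table 1 still declares 10⁻⁴, Section 10.1 still promises it, and neither Section 7.1 nor Section 10.1 discloses the change of main analysis set. The analogy with PET-CR also has a limit. For that endpoint the restriction to FDG-avid participants is written into the declared endpoint in both documents; for MRD it is not.

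**Conclusion.** The point holds as a conflict between the declared endpoint and the planned analysis, with an out-of-date and incomplete record of departures. One of two declared thresholds has no planned result, and the protocol's analysis set has none at either threshold. This rests on current text; the amendment log only explains how the mismatch arose.

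The impact is limited. MRD negativity is an other secondary endpoint outside the hierarchy, with nominal p-values (Protocol Section 10.3, SAP Section 3.2). No alpha, sample size or primary conclusion depends on it. The change of set alters the estimand and the absolute rate. The illustrated shifts of 5 to 20 points rest entirely on assumed rates and evaluable shares, and on counting participants without a clone as failures; they measure a change of denominator, not bias. A correction should still be made, because the present text cannot be followed consistently and correcting it costs little.

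**What to change.** 1. Keep 10⁻⁵ in the MRD blood-evaluable set as the main presentation.
2. Add 10⁻⁴ rows to Table 2.2.5.x, and FAS-denominator rows as a supportive summary. State how participants without an identifiable clone are counted. Label the FAS rows as the protocol's population with the SAP's choice of peripheral blood, since Protocol Section 10.4.1.4.2 names no sample type and the protocol collects both blood and marrow for MRD.
3. Correct SAP Section 10.1 to say that the main MRD analysis set departs from the protocol's FAS, and why. Add the exception to SAP Section 7.1, and list the 10⁻⁴ summary in Section 7.4.2 so that the cross-reference from Section 10.1 is valid.
4. If 10⁻⁴ is truly dropped, remove it instead from SAP Table 1, SAP Section 10.1 and Protocol Table 5, and give the reason.

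The cost is a few extra table rows from data already collected and some corrected SAP text. Only dropping 10⁻⁴ would require a change to the protocol's endpoint table.

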Efficacy assessments (s	see Section	8.2)														
Bone marrow core biopsy/bone marrow aspirate* (local)	X					X*						X‡				*If a biopsy is not clinically feasible. an aspirate should be collected. †At the time of radiologic CR only if bone marrow is involved at screening. ‡Only if bone marrow is involved at screening and morphologic CR is not seen on treatment.
Bone marrow aspirate for central MRD assessment	X					X	*					X				*At the time of radiologic CR only if bone marrow is involved at screening.
PET scan	X									X*		Х*,†		X*,†		*Only to confirm radiologic CR in FDG-avid participants. †Repeat only if no prior on-treatment PET was performed.
CT/MRI	X	Year 1 Years Years	2-3:	every	y 16 w	veeks	(4 m	$0, \pm 2$	wk)			X		X*		*Only if EOT is not due to disease progression.

Table 3: Schedule of Activities (Continued)

	Screening Period		Treatment Period]	Follow-Up P	eriod	
				Cycle 1 da							/cle 4 days ^a)		Safety Follow-Up	Efficacy Follow-Up	Survival Follow-Up	
Activities	Up to Day -1	C1D1		-	Day 22	Day 1	Day 8	Day 15	Day 22	Day 1		EOT (± 2 days)	90 Days From EOT (± 7 days)		Every 12 Weeks From EOT (± 4 weeks)	Notes
Efficacy assessments (c	•	L	 									(=, 2)	(', .,		(1	- 10000
Response assessment		Years	Year 1: every 12 weeks (3 mo, ± 2 wk) Years 2-3: every 16 weeks (4 mo, ± 2 wk) Years 4-6: every 24 weeks (6 mo, ± 3 wk)									X		X*	Χţ	
Survival status															X	
Quality-of-life assessm	ents (see Se	ection 8	3.2.5)													
EORTC QLQ-C30 questionnaire		X				X				X		X		X*		*During efficacy follow-up, questionnaires
EQ-5D-5L questionnaire		X	X X X									X		X*		must be completed at the same time as response
FACT-Lym questionnaire		X				X				X		X		X*		assessment (see above).

^a Additional visit windows will be provided in referenced sections, as appropriate.

Table 4: Schedule of Laboratory Assessments

	Screening				Tre	atmen	t Peri	od					Fo	llow-Up Per	riod	
		Cycle 1 (± 1 Day)											Safety Follow-Up	Efficacy Follow-Up	Survival Follow-Up	
Activities	Up to Day -1	C1D1	Day 8	Day 15	Day 22	Day 1	Day 8	Day 15	Day 22	Day 1	Day 15	ЕОТ	90 Days From EOT (±7 days)		Every 12 Weeks From EOT (± 4 weeks)	Notes
Laboratory assessm	ents (see Se	ction 8.	3.5)													
Hematology	X	X	X	X	X	X		X		X		X				
Clinical chemistry	X	X	X	X	X	X		X		X		X				
Coagulation	X	X				X				X		X				
C-reactive protein	X	X				X				X		X				
Urinalysis	X															Repeat if clinically indicated after screening.

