8.2.2.2. Bone Marrow Aspirate Sample Collection

A bone marrow aspirate must be collected at screening and EOT and sent to the central laboratory for MRD analysis regardless of marrow involvement status at baseline. A portion of

the first draw is preferable, but the second draw can be used if there is inadequate sample volume from the first draw.

An aspirate will need to be repeated and sent for central MRD analysis at the time of radiologic CR only if marrow is involved at screening.

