5.3. Analysis Populations

A full description of the populations for analysis is presented in Table 4.

Table 4: Analysis Populations

Population	Description
All screened	All participants who sign the ICF.
FAS	All randomized participants. Treatment groups for this population will be determined according to the treatment they were assigned at the time of randomization.
	The FAS will be used for the summary of demographics, baseline characteristics, participant disposition, and analyses of all efficacy data.
PPS	The subset of the participants in the FAS who are compliant with the requirements of the clinical study Protocol with no important Protocol deviations. All important protocol deviations or conditions leading to exclusion from the PPS will be detailed in the Protocol Deviation Specifications and identified prior to database lock for the primary analysis. Sensitivity analyses of the primary endpoint may be performed using the PPS.
MRD blood-evaluable set	All participants in the FAS who received at least 1 dose of tafasitamab/placebo, lenalidomide, or rituximab with identifiable clonality in blood sample at Cycle 1 Day1.
MRD bone marrow-evaluable set	All participants in the FAS who received at least 1 dose of tafasitamab/placebo, lenalidomide, or rituximab with either identifiable clonality in bone marrow at screening or identifiable clonality in blood sample at Cycle 1 Day 1.
SAF	All randomized participants who received at least 1 dose of tafasitamab/placebo, lenalidomide, or rituximab. Treatment groups for this population will be determined according to the actual treatment the participant received regardless of assigned treatment at the time of randomization. All safety analyses will be conducted using the SAF.
FDG-avid population	All randomized participants with a PET scan at baseline with a resulting Deauville score of 4 or 5.

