2.2.5.x	Summary of Minimal Residual Disease- Negativity Rate in Peripheral Blood at End of Treatment	MRD-blood evaluable	X	X	X	X	X	
2.2.6.x	Sensitivity Analysis for Summary of Minimal Residual Disease Negativity Rate in Peripheral Blood	MRD-blood evaluable	X		X	X	X	
2.2.7.x	Sensitivity Analysis for Summary of Minimal Residual Disease Negativity Rate in Bone Marrow	MRD-bone marrow evaluable	X		X	X	X	
2.2.8.x	Summary of Overall Response Rate by Investigator Assessment	FAS	X	X	X	X	X	
2.2.9.x	Summary of Overall Response Rate by IRC	FAS	X	X	X	X	X	
2.2.10.x	Sensitivity Analysis for Summary of Overall Response Rate by Investigator Assessment	FAS	X		X	X	X	
2.2.11.x	Summary of Duration of Response by Investigator Assessment	FAS	X	X	X	X	X	
2.2.12.x	Summary of Duration of Response by IRC	FAS	X	X	X	X	X	
2.2.13.x	Sensitivity Analysis for Summary of Duration of Response by Investigator Assessment	FAS	X		X	X	X	
2.2.14.x	Summary of Concordance Rates Between Investigator Assessment and IRC Review	FAS	X	X	X	X	X	
2.2.15.x	Summary of Currentness of Progression- Free Survival and Overall Survival	FAS	X		X	X	X	
2.2.16.x	Summary of Progression-Free Survival and Overall Survival Follow-Up Time	FAS	X		X	X	X	
2.2.17.x	Summary of Quality of Life Assessments - EORTC QLQ-C30	FAS	X		X	X	X	
2.2.18.x	Summary of Quality of Life Assessments - EQ-5D-5L	FAS	X		X	X	X	
2.2.19.x	Summary of Quality of Life Assessments - FACT-Lym	FAS	X		X	X	X	
2.3.3.x	Summary of Post-Treatment Systemic Antilymphoma Therapies	FAS	X		X	X	X	

Table No.	Title	Pop	FL	MZL	Overall	Jap FL	Jap Overall	Standard
		ı		1	1	ı	ı	ı
2.90.4.x	Summary of Progression-Free Survival by Investigator Assessment in PPS	PPS	X	X	X	X	X	
2.90.8.x	Summary of Overall Survival in PPS	PPS	X	X	X	X	X	
Safety								
3.1.1.x	Summary of Exposure to Tafasitamab/Placebo	SAF	X	X	X		X	X
3.1.2.x	Summary of Exposure to Rituximab	SAF	X	X	X		X	X
3.1.3.x	Summary of Exposure to Lenalidomide	SAF	X	X	X		X	X
3.1.4.x	Summary of Exposure to Lenalidomide by Creatinine Clearance	SAF	X	X	X		X	X
3.2.1.x	Overall Summary of Treatment- Emergent Adverse Events	SAF	X	X	X		X	X
3.2.2.x	Summary of Treatment-Emergent Adverse Events by MedDRA SOC and	SAF	X	X	X		X	X
3.2.3.x	Preferred Term Summary of Treatment-Emergent	SAF	X	X	X		X	X
	Adverse Events by MedDRA Preferred							
3.2.4.x	Term in Decreasing Order of Frequency Summary of Treatment-Emergent	SAF	X	X	X		X	X
	Adverse Events by MedDRA SOC, Preferred Term, and Maximum Severity							

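### The denominator for the bone-marrow MRD rate at CR includes participants from whom the protocol never requires a CR marrow sample

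*SAP*

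**What the plan says.** **Analysis.** The main MRD rate in SAP Section 7.4.2 is negativity in peripheral blood at EOT. Three sensitivity analyses follow: blood at Cycles 4 and 8, marrow at EOT, and marrow at CR. The last is worded "Using bone marrow sample at CR (in the MRD-bone marrow evaluable population"). Appendix A lists one marrow table, 2.2.7.x, "Sensitivity Analysis for Summary of Minimal Residual Disease Negativity Rate in Bone Marrow".

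**Denominator.** SAP Section 5.3, Table 4, defines the marrow-evaluable set as treated FAS participants "with either identifiable clonality in bone marrow at screening or identifiable clonality in blood sample at Cycle 1 Day 1". It sets no condition on lymphoma involvement of the marrow or on reaching CR.

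**Sampling.** Protocol Section 8.2.2.2 has a repeat aspirate "sent for central MRD analysis at the time of radiologic CR only if marrow is involved at screening". The central MRD row of the schedule of activities (Table 3) has the same restriction: "At the time of radiologic CR only if bone marrow is involved at screening". The other two timepoints differ: "A bone marrow aspirate must be collected at screening and EOT and sent to the central laboratory for MRD analysis", whatever the baseline marrow status.

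**Absent results.** The paragraph defining the blood rate at EOT says: "Participants with no postbaseline assessment, or who did not achieve a negative MRD result will be classified as" non-MRD-negative. The rule is not restated for the sensitivity analyses. Reasons for missing assessments will be summarized; the two examples given are missed and unevaluable assessments.

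**The concern.** A participant whose marrow is uninvolved at screening but who has a detectable clone belongs to the marrow-evaluable set. If that participant reaches radiologic CR, no marrow aspirate is due. The sample is absent by design, so the participant can lower the reported rate but never raise it.

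The figure then depends partly on how many participants had involved marrow at baseline, which says nothing about treatment. Marrow involvement is not a stratification factor in either cohort, so a chance imbalance would shift the rates by arm even if marrow clearance were the same. The EOT and CR marrow rates share one population label and apparently one table, although nearly everyone is due a sample at EOT and only a subgroup at CR. A reader could take the gap between them for biology.

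**Working it through.** The documents give no MRD rate, no marrow-involvement share, no CR share and no size for the evaluable set, so there is no plan figure to reproduce. The check compares the denominator with the sampling rule and works out the dilution.

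**Who is counted and who is sampled at CR**

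| Participant in the marrow-evaluable set | In SAP denominator | CR aspirate due |
|---|---|---|
| Marrow involved, radiologic CR | yes | yes |
| Marrow involved, no CR | yes | no (no CR) |
| Marrow uninvolved, radiologic CR | yes | **no (sampling rule)** |
| Marrow uninvolved, no CR | yes | no (both reasons) |

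The mismatch lies in the two uninvolved rows. The second row is a separate matter: counting a participant who never reaches CR as a failure is a legitimate composite definition.

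**Notation (all values are assumptions)**

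- q = share of the evaluable set with marrow involved at screening
- c = share of those with involved marrow who reach radiologic CR
- r = share MRD-negative among those sampled at CR

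Assume every sample that is due is obtained and evaluable.

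**Three rates obtainable from the same data**

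- Whole evaluable set, absent results counted as non-negative: q × c × r
- Marrow-involved participants only, non-CR counted as non-negative: c × r
- Sampled participants only: r

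The first divided by the second is q. That factor is the whole effect of the mismatch.

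**Dilution at c = 0.5 and r = 0.8**, so c × r = 0.40

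| q | q × c × r | Marrow-involved denominator |
|---|---|---|
| 0.3 | 12% | 40% |
| 0.5 | 20% | 40% |
| 0.7 | 28% | 40% |
| 0.9 | 36% | 40% |
| 1.0 | 40% | 40% |

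With r = 0.8, q from 0.3 to 0.9 and c from 0.3 to 0.7, the whole-set rate runs from 0.3 × 0.3 × 0.8 = 7.2% to 0.9 × 0.7 × 0.8 = 50.4%. The marrow-involved rate runs from 0.3 × 0.8 = 24% to 0.7 × 0.8 = 56%.

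**Chance imbalance in q.** With c × r = 0.40 in both arms and q = 0.50 against 0.55, the reported rates are 0.50 × 0.40 = 20% and 0.55 × 0.40 = 22%. The two-point gap comes from baseline involvement alone.

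**What is not due to the mismatch.** Take q = 0.45 and r = 0.80 in both arms, with CR in 40% against 55%.

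- Whole set: 0.45 × 0.40 × 0.80 = 14.4% against 0.45 × 0.55 × 0.80 = 19.8%
- Marrow-involved: 0.40 × 0.80 = 32% against 0.55 × 0.80 = 44%

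Both ratios are 0.727 (14.4/19.8 and 32/44). An arm difference driven by CR is present under either denominator.

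**The case against.** The strongest reply is that this is a clarification with little consequence. MRD is a non-key secondary endpoint, the analysis is one of three sensitivity analyses, the SAP plans only a rate and exact interval by arm with no comparison, and it lies outside the testing hierarchy in SAP Section 3.2. All of that stands and limits the weight of the point.

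The second reply is that the non-negative rule is written for blood at EOT, and the SAP does not say that it extends to marrow at CR. That also stands, so the dilution is conditional. It does not clear the plan: the stated population still contains people never due a sample, and without a rule two programmers could report q × c × r or r from the same data.

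Third, reasons for missing assessments and baseline marrow involvement (SAP Section 6.1.2) will both be summarized, so an attentive reader could see why samples are absent. This helps interpretation but leaves the denominator unchanged.

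Three stronger readings are tempting and are not supported:

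- *The rate cannot be derived.* It can, once the non-negative rule is applied.
- *The rate will be far too low.* That needs q, which the documents do not give. Because the set is selected for a detectable clone, involvement in it may be higher than among all participants.
- *The mismatch produces an arm difference that merely reflects CR rates.* As shown above, that difference remains when the denominator is corrected; it comes from counting non-CR as failure.

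**Conclusion.** The point holds as a mismatch between denominator and sampling rule. As written, the analysis set includes participants who cannot contribute a CR marrow result. If absent results count as non-negative, the rate is reduced by the factor q. The direction is certain for any q below 1, and some uninvolved participants are to be expected, since the protocol provides for aspirates from them at screening and EOT. The size is unknown: a tenth of the rate is lost at q = 0.9, half at q = 0.5 and 70% at q = 0.3.

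The conclusion rests on two assumptions: the non-negative rule extends to this analysis, and CR aspirates are taken only as the protocol requires. It is confined to one descriptive, untested sensitivity analysis. The main MRD analysis in blood at EOT is unaffected, as is the marrow analysis at EOT, where an aspirate is required regardless of involvement.

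**What to change.** In SAP Section 7.4.2 and Table 2.2.7.x:

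1. Restrict the denominator of the CR analysis to marrow-evaluable participants whose marrow was involved at screening. This is fixed at baseline and matches Protocol Section 8.2.2.2.
2. State that, within that group, participants without CR and those with a missing or unevaluable CR sample count as non-negative.
3. In the summary of missing assessments, tabulate samples not required by protocol separately from missed or unevaluable ones.
4. If a rate among participants with a CR aspirate is also shown, label it descriptive, because it conditions on a post-randomization outcome.
5. Leave the EOT marrow analysis on the full marrow-evaluable set.

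The cost is a few sentences in the SAP and a programming filter. Protocol Section 8.2.2.1 already requires local marrow results in the eCRF, so no new samples or data are needed. The denominator shrinks to the fraction q of the present one, so the exact confidence interval will be wider.
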